**6.5. Pre-registration / Determination of Eligibility (Visit 1)**

The study surgeon will perform the initial determination of eligibility when he sees his patients at preoperative clinic. He will inform potentially eligible subjects about the study and ask them if they would be willing to meet with the study coordinator. The study coordinator will attend the surgeon's preoperative clinic and, during the clinic, meet briefly with willing subjects. This brief meeting will represent Visit 1, the pre-registration visit. At this pre-registration visit, the coordinator will outline the research protocol to the subject; give the subject an informational flyer, an MRI screening safety questionnaire,

and a consent form; ask for the subject's verbal permission to confirm eligibility by reviewing relevant medical records under the supervision of the surgeon; record the subject's preferred contact information; and schedule the subject for a registration visit.

**6.6. Registration Visit (Visit 2)**

At the registration visit, the coordinator will explain the protocol in greater detail and answer the potential subject's questions. The MRI screening questionnaire and consent form will be reviewed. With the subject's verbal permission, eligibility criteria will be rechecked. If the eligibility criteria are met, the subject will be asked to sign informed consent and the subject will be registered in the trial. The research coordinator will record demographic data (gender, date of birth, self-reported ethnicity, and self-reported racial group) as well as clinical and laboratory data related to the eligibility criteria (diagnosis of CRC metastases to liver, absence of history of nephrogenic systemic fibrosis, and eGFR). If an eGFR obtained for clinical care is not available within 35 days of the scheduled hepatectomy, then a serum eGFR laboratory test will be ordered. The serum sample will be obtained by a certified phlebotomist or other qualified medical professional as a study procedure. The coordinator will schedule the research MRI examination and review with the subject pre-MRI instructions.

**6.7. Reminder Phone Call (Visit 3)**

Within one week prior to the MRI, the coordinator will call the patient to remind him or her about the MRI appointment. The coordinator will briefly review the MRI instructions and answer any questions.

**6.8. Research MRI (Visit 4)**

The research MRI will be done 2-10 days prior to the scheduled hepatectomy. The research coordinator and technologist will meet the subject upon arrival at the MR3T facility and confirm consent, re-review MR safety screening questionnaire, obtain a urine pregnancy test (if the subject is a woman of child bearing potential), and weigh the subject (to determine the appropriate contrast agent dose). The MRI examination will be performed (see Section 6.11). The PI or study investigator will monitor each MR examination and observe the subjects for adverse events until the subjects leave the MR facility. Adverse events will be recorded on an adverse event form (Section 8.0). Immediately prior to discharge from the MR facility, subjects will be given compensation as detailed in the consent form.

**6.9. Pre-operative Admission/Post-MRI Visit (Visit 5)**

The study surgeon will admit the subject to the hospital prior to hepatectomy. At the time of pre-operative admission, the surgeon will ask the subject about any delayed adverse events that occurred after the research MRI. This will represent Visit 5 for this trial. The surgeon or his representative or the will record the adverse event information on a data entry sheet.

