**6.4. Study Calendar / Schedule**

Study procedure	Visit 1 Pre- registration	Visit 2 Registration	Visit 3 Phone call within 1 week prior to MRI	Visit 4 MRI 2-10 days prior to hepatectomy	Visit 5 Admission to hospital for hepatectomy	Hepatectomy and specimen imaging
Determine eligibility	X	Confirm eligibility				
Review MRI safety	X			X		
Give info. flyer	X					
Obtain consent		X		Confirm consent		
Register subject		X				
Collect demo. data		X				
Serum sample		*				
Review instructions		X	X	X		
Subject reminder			X			
Pregnancy test				*		
Weigh subject				X		
Insert IV catheter				X		
Research MRI				X		
Acute AE monitoring				X		
Compensate subject				X		
Delayed AE monitoring					X	
Standard of care therapy					X	X
Ex-vivo MRI						X

\* = select subjects

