**6.10. Criteria for Removal from Study**

Registered subjects will be withdrawn from the study if any of the following conditions are met:

- 6.10.1. Research MRI is not performed
- 6.10.2. Intravenous access cannot be established.
- 6.10.3. eGFR < 45 on blood sample drawn after registration
- 6.10.4. Subject has a positive urine pregnancy test after registration.
- 6.10.5. Hepatectomy is not performed.
- 6.10.6. Subjects withdraws his/her consent.
- 6.10.7. Exclusion criteria are discovered after registration but prior to MRI

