  - Dynamic 3D T1w LAVA: TR min, TE min, matrix 320x224, FA 15, slice thickness 4 mm, bandwidth 100 kHz, parallel imaging on (acceleration factor = 2). Options: SCIC, extended dynamic range, zip 2, zoom gradient (if FOV ≤ 35 mm). Obtain before and 20,

80, and 180 seconds after injection of 0.1 mmol/kg gadobenate dimeglumine (MultiHance, Bracco) at 2 ml/sec followed by 20 ml saline flush. Same FOV as Image Set 1.

- **Image Set 8.**
  - Late venous phase LAVA: 5 minutes. Same FOV and other parameters as Image Set 7.
- **Image Set 9.**
  - Hepatocellular phase LAVA: 60 minutes. Same FOV and other parameters as Image Set 7.

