### **7.0.2. Parametrized data**

Standardized data entry forms will be designed for each type of data being collected:

- Subject identifiers and demographics
- Subject lab results (e.g., eGFR, urine pregnancy test)
- List of sequences acquired and repeated during the pre-hepatectomy examination
- Adverse events occurring during the MRI appointment
- Adverse events occurring during first 24 hours after Gd injection as recorded by the study surgeon at subject admission for surgery.
- Lesion cross reference table
- Lesion reference standard table
- MRI features for each lesion

The research coordinator or study investigator will manually enter data into the corresponding data forms. Completed data entry forms will be duplicated. One set will be kept with each subject's research chart. One set will be kept in folders with other forms of the same type. The coordinator will transfer the data from the entry forms into an electronic database. The database is password protected, maintained by a data manager at the MR3T facility, stored on two servers, backed up to external hard-drives every 24 hours.

For statistical analysis, the database program will generate de-identified spreadsheet reports containing the variable of interest to the study statistician.

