### **8.4.2. Documentation**

The PI will document all Adverse Events (AEs) that within the first 24 hours following contrast injection. This time period exceeds 10 elimination half-lives of gadobenate dimeglumine [MulthiHance product insert]).

AEs will be recorded within the study participant's chart within one week of the PI becoming aware of the event. The nature of each event, date and time (when appropriate) of onset, outcome, frequency, maximum intensity, action taken, and attribution will be recorded.

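### Adverse events in the 24 hours after contrast have no planned enquiry, once the subject has left the MR facility, if surgery is cancelled before admission

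*Protocol*

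**What the plan says.** Section 8.4.2 makes the commitment: "The PI will document all Adverse Events (AEs) that within the first 24 hours following contrast injection". The sentence lacks a verb, but its sense is clear. It is not restricted to subjects who go on to surgery, and the same section justifies the window by the contrast agent's elimination half-life, so the clock belongs to the injection.

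The capture steps are spread over several sections:

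- Section 6.8 has the PI or a study investigator "observe the subjects for adverse events until the subjects leave the MR facility".
- Section 6.9 (Visit 5) says that, at pre-operative admission, "the surgeon will ask the subject about any delayed adverse events that occurred after the research MRI".
- The calendar in section 6.4 has a row "Delayed AE monitoring", marked only under Visit 5.
- Section 7.0.2 lists the corresponding data form as "Adverse events occurring during first 24 hours after Gd injection as recorded by the study surgeon at subject admission for surgery".
- On timing, section 6.8 states: "The research MRI will be done 2-10 days prior to the scheduled hepatectomy".
- Section 6.10 lists, among the conditions for withdrawing a registered subject, "Hepatectomy is not performed".

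**The concern.** The commitment is tied to the injection, but the only planned means of meeting it after discharge is tied to a surgical admission. The protocol itself expects that some operations will not take place. It also describes a route by which plans could change after contrast has been given: under section 10.1 the PI passes major unexpected MRI findings that could affect management to the surgery team.

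What is at stake is the completeness of a stated safety record. If the plan is followed exactly as written, some subjects exposed to contrast could have nothing on file for most of the promised window, and a blank form could not be told apart from an absence of events.

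**Working it through.** The protocol states no figure for this point that could be reproduced. The check sets the sections side by side, with some arithmetic on timing.

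**Inputs**

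- Documentation window: 24 hours from injection (8.4.2).
- End of direct observation: departure from the MR facility (6.8).
- Last acquisition: "Hepatocellular phase LAVA: 60 minutes" (MR protocol, under 6.11.2.4). This fits the timetable given there: late venous images at 5 minutes plus a 55-minute break = 60 minutes after injection.
- MRI to scheduled hepatectomy: 2 to 10 days (6.8).
- Planned enrolment: 30 (Protocol Overview; 6.3).

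**Step 1. How much of the window is observed.** A subject who completes the examination is observed for about 1 hour after injection, plus any further stay. The remainder is 24 − 1 = 23 hours, and 23/24 = 0.958, or about 96% of the window.

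**Step 2. When the remainder is asked about.** The window closes 1 day after the MRI. Relative to the scheduled operation that is 2 − 1 = 1 day to 10 − 1 = 9 days beforehand. Admission may precede the operation date, so the gap to Visit 5 may be somewhat shorter.

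**Step 3. Whether any other contact fills the gap.** The only scheduled call, Visit 3 (6.7), comes before the MRI. Section 9.5 has the PI monitor adverse events but specifies no subject contact. The form in 7.0.2 is itself completed at admission. No other contact after the MRI is described.

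**Step 4. What happens on each path.**

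- Contrast given, admitted, resected: asked at Visit 5.
- Contrast given, admitted, not resected: Visit 5 comes before surgery, so the subject has been asked.
- Contrast given, surgery cancelled before admission: withdrawn under 6.10.5, with no Visit 5. No enquiry is planned for the roughly 23 hours after discharge.
- Contrast not given (for example, no MRI or no intravenous access): the window never opens.

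Only the third path has the gap.

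**Step 5. How many subjects.** The protocol gives no cancellation rate, so this is an assumed range applied to all 30:

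- 30 × 0.05 = 1.5
- 30 × 0.10 = 3
- 30 × 0.20 = 6

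The base of 30 is an upper limit, because some enrolled subjects may never be injected.

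**The case against.** The strongest defence is that this is a small single-site pilot, described in section 9.5 as minimal risk, in which the study surgeon's own patients are asked about events by that surgeon. An event serious enough to stop an operation would probably reach the surgeon. Section 8.4.2 requires recording within one week of the PI becoming aware of an event, whatever the source, so a spontaneous report would be documented. No endpoint concerns safety. All of this stands, and it limits the weight of the point. It does not supply the missing enquiry: documenting what happens to be reported is less than documenting all events.

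A reader might infer more than the protocol supports:

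- *That every subject without a hepatectomy is never asked.* Visit 5 takes place at admission, so only cancellation before admission is affected, and what is missing is a planned enquiry.
- *That the missing subjects are those most likely to have had events.* Nothing in the protocol shows this. It is possible, but given the surgeon's role the opposite is also plausible.
- *That the gap weakens an estimated adverse event rate.* The protocol plans no such rate or bound, so there is no analysis to be weakened.
- *That the windows contradict each other.* The open question in 6.9 contains the 24-hour period in 7.0.2 and 8.4.2. A broad question with a narrower recording window is workable, although the text leaves unclear whether later events are recorded.
- *That asking up to 10 days later is itself a failure.* It is a stated design choice, and the protocol offers no evidence that recall over that interval is inadequate.
- *That withdrawn subjects' safety data are discarded.* Section 6.10 withdraws subjects but does not say this.

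**Conclusion.** The point holds in a narrow form. As written, the plan cannot assure the capture promised in section 8.4.2 for subjects who receive contrast and whose surgery is cancelled before admission. For them about 23 of the 24 hours have no planned enquiry.

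This rests on two readings: that observation ends soon after the 60-minute images, and that no post-MRI contact exists beyond those described. A longer stay at the facility would reduce the 23 hours but would not close the gap. The number of subjects is unknown, and the range of about 1.5 to 6 reflects assumed cancellation rates only. Sensitivity, specificity, ROC area and repeatability are unaffected. Severity is minor: a safety commitment and its procedure need to be brought into line.

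**What to change.** Amend sections 6.4, 6.9, 7.0.2 and 8.4.2 so that the existing coordinator completes the 24-hour adverse event form by telephone, once the window has closed, for every subject who received contrast, whether or not hepatectomy takes place. Subjects who have withdrawn consent to further contact (6.10.6) must be exempt. The Visit 5 question can remain as a second check.

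In section 6.9, state that the events to be recorded are those in the window used in 7.0.2 and 8.4.2, or otherwise reconcile the three sections.

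The cost is one short call per subject and a small amendment. No extra visit or staff is needed, since the coordinator already makes the reminder call at Visit 3.

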**6.10. Criteria for Removal from Study**

Registered subjects will be withdrawn from the study if any of the following conditions are met:

- 6.10.1. Research MRI is not performed
- 6.10.2. Intravenous access cannot be established.
- 6.10.3. eGFR < 45 on blood sample drawn after registration
- 6.10.4. Subject has a positive urine pregnancy test after registration.
- 6.10.5. Hepatectomy is not performed.
- 6.10.6. Subjects withdraws his/her consent.
- 6.10.7. Exclusion criteria are discovered after registration but prior to MRI

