### **6.11.3. Pre-hepatectomy MR imaging interpretation**

#### 6.11.3.1. Overview.

The study radiologist will have expertise in MRI of the liver. The radiologist will be trained on a test set to become familiar with the imaging criteria. After the training, the radiologist will review and interpret the pre-hepatectomy research exams. The radiologist will know the subject's study ID and date of birth, and will be aware that the subject has a pre-operative diagnosis of CRC metastasis to the liver. The coordinator will explain to the radiologist the segment(s) that were resected at surgery. The radiologist will be blinded to all other information. MR images (test set and research exams) will be reviewed on high-resolution >4 megapixel gray-scale monitors using the hospital PACS system.

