#### 6.11.3.3. Interpretation.

The radiologist will review the nine image sets in a different random order in one reading session for each subject. (Reviewing each image set in a different session is not feasible). The random order of review will reduce bias in the performance of one image set relative to another. During the review of each image set, the radiologist will flag each detected nodule, number each new nodule consecutively, and characterize the corresponding nodule feature(s) as outlined in the Table below. If the radiologist identifies nodules on one image set that were missed on a prior image set, the radiologist will re-review the prior image set and retrospectively characterize the corresponding nodule features. The initial interpretations will be used for specific aim 1 and the final interpretations for specific aim 2. After the nine image sets are reviewed, the radiologist will review all the images in conjunction and score ten global lesion features. The radiologist also will score two per-patient features (anterioposterior skin-to-skin diameter of the abdomen [contiguous] and presence of ascites [four-point ordinal: none, mild, moderate, severe]), as these may conceivably affect image quality.

The research coordinator will enter the radiologist's per-lesion and per-patient interpretations into a data entry sheet. Representative screen capture images showing the

location and identifier of each lesion detected by the study radiologist will be exported in JPEG format. Under the radiologist's supervision, the research coordinator will place regions of interest on image sets 4-6 and record the T2\*, ADC, shear modulus values for each nodule and for each of the repeated acquisitions. Both repeated measurements will be used in the analysis of intraclass correlation coefficient. Only the first of the repeated measurements will be used in the sensitivity, specificity, and ROC analyses.

Image Set	Feature	Categories
1 T2w SSFSE	Signal intensity	Homogeneous 
 
• Markedly hypo-intense
 
• Hypo-intense
 
• Iso-intense
 
• Hyper-intense
 
• Markedly hyper-intense
 
 Heterogeneous
2 T2w FRFSE	Signal intensity	Homogeneous 
 
• Markedly hypo-intense
 
• Hypo-intense
 
• Iso-intense
 
• Hyper-intense
 
• Markedly hyper-intense
 
 Heterogeneous

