## **9.0 STATISTICAL CONSIDERATIONS**

### **9.1 Study Design and Endpoints**

#### **9.1.1. General study design.**

This is a prospective cohort pilot study assessing 3T MRI for diagnosis of CRC metastases to the liver in pre-hepatectomy patients. Consecutive eligible subjects with CRC metastases to the liver will undergo a research MRI of the liver within one week prior to curative hepatectomy done for clinical care. One radiologist will review the MR images and, for each focal lesion (benign or malignant) identified at imaging on each subject, assess 21 imaging features such as size, shape, margination, heterogeneity, kinetic enhancement pattern, and overall confidence for malignancy. Features will include binary, categorical, ordinal, and continuous variables. Sixteen features will be standard and five (T2\*, ADC, shear modulus, late venous phase signal intensity, and hepatocellular phase signal intensity) will be experimental. The MR sequences used to obtain the three quantitative experimental lesion features (T2\*, ADC, shear modulus) will be acquired twice for each subject. The radiologist also will assess two-per patient imaging features (abdominal AP diameter at the level of the portal vein bifurcation and the presence of ascites). Three demographic features (subject age, gender, ethnicity) will be available for the multivariate analyses; of the three, age will potentially be known to the radiologist as the scans will include the subject's date of birth.

For each subject, the lesions included in the analysis will be those identified at pre-hepatectomy imaging, *ex-vivo* imaging, pathology, or any combination of the three. The reference standard for each lesion will be the dichotomized histological diagnosis (malignancy versus other). Subjects are expected to have between one and ten CRC metastases in the hepatectomy specimen (average of three) and zero to five benign lesions (average of one). Subjects are not expected to have any malignancies other than CRC metastases.

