**9.1.2.2. Secondary aims.**

9.1.2.2.1. Secondary aim 1.

9.1.2.2.1.2. Aim.

Estimate and compare the per-lesion area under the ROC curve of a multivariate model that uses experimental as well as standard MRI features versus that of a model that uses only standard MRI features for the diagnosis of CRC metastases. Both models may use per-patient features such as age, gender, ethnicity, ascites, and anteroposterior diameter.

9.1.2.2.1.2. Analysis plan for secondary aim 1.

Using all available per-lesion MRI features (standard and experimental), per-subject MRI features (anteroposterior diameter and ascites), and per-subject clinical features (age, gender, ethnicity), multivariate models will be constructed to assess the discriminatory ability of each MRI feature after adjusting for the other features.

Other multivariate models will be constructed after excluding experimental features from consideration.

The area under the ROC curves corresponding to these models will be compared. To account for clustering due to multiple lesions for some patients and multiple observations per lesion, generalized estimating equation techniques will be used. The model with the largest area under the ROC curve will be identified.

9.1.2.2.2. Secondary aim 2.

9.1.2.2.1. Aim: Estimate the intraclass correlation coefficient of repeated quantitative measurements (T2\*, ADC, and shear modulus) on each lesion.

9.1.2.2.1.2. Analysis plan for secondary aim 2. The intra-class correlation coefficient between repeated measures will be calculated.

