**10.0 Regulatory and Ethical Considerations**

**10.1 Protection of Patient Rights**

The PI, a liver radiologist, will monitor MR examinations and report any major, unexpected findings that may alter clinical management to the surgery team. The PI and the surgery team in consensus will formulate a list of findings to be reported. Patients will be informed of this possibility at the time of consent.

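### Section 6.10.5 withdraws unoperated subjects from the whole study, although their completed repeat MRI data are all that secondary aim 2 needs

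*Protocol*

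**What the plan says.** The removal rule in Section 6.10 applies to the study as a whole: "Registered subjects will be withdrawn from the study if any of the following conditions are met". Among the conditions is "6.10.5. Hepatectomy is not performed". Nothing in the section separates one aim from another or says what becomes of data already collected.

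The scan comes before this condition can arise. Section 6.8 states: "The research MRI will be done 2-10 days prior to the scheduled hepatectomy". In the MR protocol of Section 6.11.2, Image Sets 4 to 6 (T2*, ADC, shear modulus) are each acquired and then repeated within that one examination.

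On the use of the repeats, Section 6.11.3.3 says "Both repeated measurements will be used in the analysis of intraclass correlation coefficient" and reserves the first measurement alone for the sensitivity, specificity and ROC analyses. The plan for secondary aim 2 in Section 9.2 is a single sentence: "The intra-class correlation coefficient between repeated measures will be calculated".

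The reading procedure in Section 6.11.3.1 assumes that an operation has taken place: "The coordinator will explain to the radiologist the segment(s) that were resected at surgery". No reading is described for a subject who was scanned but not resected.

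**The concern.** The rule suits the primary aim and secondary aim 1, because without a specimen there is no reference standard. It does not suit secondary aim 2, which compares a measurement with its own repeat. A subject whose surgery is cancelled after the MRI has nothing missing for that aim, yet is removed from it by a condition unrelated to whether repeatability can be measured.

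Two steps lead to the loss. Section 6.10 takes the subject out of the study. Independently, the regions of interest that yield the T2*, ADC and shear-modulus values are placed under the radiologist's supervision during a reading organised around resected segments. If that reading is not done for an unoperated subject, there are images but no values.

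At stake is some precision in one of the two secondary endpoints of a pilot whose purpose is to plan a later trial. These subjects have already had an examination of about 90 minutes with contrast, so leaving valid data unused is also a poor return on their participation.

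**Working it through.** **1. Does secondary aim 2 need anything that an unoperated subject lacks?**

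- Two acquisitions of each sequence: available, since the MRI precedes surgery (Sections 6.8 and 6.11.2).
- A lesion to measure: available. Section 9.1.1 states "For each subject, the lesions included in the analysis will be those identified at pre-hepatectomy imaging" and goes on to allow identification by ex-vivo imaging, pathology or any combination, so a lesion seen on the MRI alone qualifies.
- Histology, specimen or ex-vivo image: not used in the ICC plan (Section 9.2).
- A reading with regions of interest: could be done, but is described only for resected subjects (Section 6.11.3.1).

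Only the last item stands in the way, and it is a matter of procedure.

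**2. The plan's own precision figure.** Section 9.3 gives a worst-case half-width of 18 percentage points for a sensitivity of 50% with 30 subjects: 1.96 × √(0.25/30) = 0.179. The figure reproduces. It concerns sensitivity; the protocol states no precision for the ICC.

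**3. Inputs for the ICC**

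- From Section 9.3: 30 subjects, four lesions each on average (30 × 4 = 120 lesions), within-subject correlation 0.5.
- Assumed, because the protocol is silent: all 30 subjects are scanned; 5% to 20% of them are then not resected (1.5 to 6 subjects, about 6 to 24 lesions); true ICC 0.8.

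**4. Formula.** The large-sample 95% half-width for an ICC r with k = 2 repeats on n lesions is

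1.96 × √[2(1 − r)²(1 + r)² / (2(n − 1))] = 1.96 × (1 − r²)/√(n − 1).

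With r = 0.8 the numerator is 1.96 × 0.36 = 0.7056.

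Three values of n cover the range of clustering:

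- 120, if lesions are independent;
- 48, after a design effect of 1 + (4 − 1) × 0.5 = 2.5, since 120/2.5 = 48;
- 30, one effective lesion per subject.

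**5. Results**

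| Effective n with all subjects kept | Nobody lost | 5% lost | 10% lost | 20% lost |
|---|---|---|---|---|
| 120 | 0.065 | 0.066 | 0.068 | 0.072 |
| 48 | 0.103 | 0.106 | 0.109 | 0.115 |
| 30 | 0.131 | 0.135 | 0.138 | 0.147 |

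The relative widening hardly depends on the row or on the assumed ICC, because it is close to the square root of the ratio of sample sizes: √(1/0.95) = 1.026, √(1/0.90) = 1.054, √(1/0.80) = 1.118. That is about 3%, 5% and 12%.

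**The case against.** **The protocol does not order the data to be discarded, and a separate analysis set may be defined in a statistical analysis plan that is not shown.** The first part is true: the loss follows from the plain reading of removal without an exception, not from an explicit instruction. The second part does not settle the matter. Withdrawal and the conduct of the reading are protocol rules, and they decide whether the values are recorded at all. An analysis plan cannot analyse measurements that were never made.

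**One cohort with histologically referenced lesions for every aim is a defensible choice.** This stands in part. Including unoperated subjects brings lesions without histological confirmation into the ICC, which is a reason to report it both ways. It is not a reason to leave out measurements whose repeatability does not depend on the diagnosis.

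**The effect is small.** This stands. One secondary aim is touched, the widening is modest, and the protocol sets no precision target for the ICC.

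Two stronger readings are tempting, and the documents support neither.

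- *The ICC is selectively lowered.* A reader might infer that unresected subjects have the most extensive disease, so that losing them narrows the spread between lesions and pulls the ICC down. If between-lesion variance fell by 20%, an ICC of 0.80/(0.80 + 0.20) = 0.80 would become 0.64/(0.64 + 0.20) = 0.76. But the protocol gives neither the reasons for non-resection nor any link between disease extent and these three measurements. With equal variance within groups and a fraction p lost, a 20% cut requires p(1 − p)d² = 0.25, where d is the difference in means in within-group standard deviations. That gives d = 0.5/√(0.1 × 0.9) = 1.67 at 10% lost and 0.5/√(0.2 × 0.8) = 1.25 at 20% lost. Nothing supports differences of that size. If the lost lesions resemble the rest there is no bias, and if they vary less than the rest the ICC could rise. Some selection is conceivable, because Section 10.1 has the principal investigator "report any major, unexpected findings that may alter clinical management to the surgery team", so the MRI might contribute to a cancelled operation. Its direction and size remain unknown.
- *The same loss occurs under 6.10.2, failed venous access.* Image Sets 4 to 6 do precede contrast. However, the subject preparation text in Section 6.11.2 and the calendar in Section 6.4 place catheter insertion before scanning, so failed access would arise before those sets exist.

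**Conclusion.** The point holds as a modest, avoidable loss of precision in secondary aim 2. As written, 6.10.5 removes subjects who have complete repeat acquisitions from an endpoint that needs no histology, and the described reading gives no route for recording their values. At an assumed non-resection rate of 5% to 20%, the ICC interval is about 3% to 12% wider than it need be; with an ICC of 0.8 and the design-effect sample, the half-width goes from 0.103 to between 0.106 and 0.115. The result rests on that assumed rate, on all 30 subjects being scanned, and on reading removal from the study as covering data already collected. Bias in the ICC is possible but cannot be signed or sized from the protocol. The primary aim and secondary aim 1 are not affected. The change is worth making because it costs so little.

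**What to change.** - **Section 6.10:** limit 6.10.5 to the sensitivity, specificity and ROC analyses, that is, the primary aim and secondary aim 1. State that, subject to consent, the completed repeat acquisitions of an unoperated subject are still read, regions of interest are placed on both, and the subject enters secondary aim 2.
- **Section 6.11.3.1:** add that for an unoperated subject the reading is done without reference to resected segments.
- **Section 9.2, secondary aim 2:** define the analysis set as all subjects with both acquisitions of the sequence concerned, whether or not operated on, and report the ICC also in operated subjects only.

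The cost is a few sentences and a few additional reads of examinations already acquired, with no new scan, procedure or subject. The downside is that some lesions in the ICC will lack histological confirmation; the second report, in operated subjects only, shows whether that matters.
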